11.7. Data Review Committee

Data Review Committee

An internal DRC will be commissioned for this study, comprised of sponsor personnel not directly involved in the conduct of the study, who have expertise in clinical study conduct and vaccines. It will consist of at least one medical expert in the relevant therapeutic area and at least one statistician.

The DRC will convene if an effect is seen on immune responses to the seasonal influenza vaccine with concomitant administration based on the immunogenicity analysis at 28 days after the first dose. An independent unblinded statistician and unblinded biomarker representative will present data to the DRC if there is an effect on immune responses to the seasonal influenza vaccine when administered concomitantly with Ad26.RSV.preF. The DRC will decide if subjects should be offered repeat influenza immunization.

The DRC will also convene to discuss any significant or unexpected safety issues. The principal investigator (PI) and study responsible physician (SRP) will inform the DRC of any AE of concern.

After safety reviews, the DRC will make recommendations regarding the continuation of the study. The conclusions of the DRC will be communicated to the investigators, the IRB/IEC and the national regulatory authorities as appropriate. Details will be provided in a separate DRC charter.

If deemed necessary for safety review, the DRC may request the randomization codes and review unblinded data, if applicable.

11.8. Study Vaccination Pausing Rules

The PI and the SRP will monitor the study vaccination pausing rules. If study vaccination is considered to raise significant safety concerns, further vaccination of subjects will be suspended until DRC review is carried out and subsequent communication between the sponsor and the investigator takes place.

The occurrence of any of the following events will lead to suspension of further study vaccination, and trigger a meeting of the DRC to discuss study suspension, adaptation or discontinuation of further vaccination:

1. One or more subjects experience an SAE or other potentially life-threatening (Grade 4) event that is determined to be related to study vaccine; *OR*
2. One or more subjects experience anaphylaxis clearly not attributable to other causes than vaccination with study vaccine; *OR*

3. Two or more subjects experience a Grade 3 or 4 unsolicited AE of the same type, determined to be related to study vaccine, that persists for 72 hours or longer; *OR*
4. Two or more subjects experience a Grade 3 or 4 solicited systemic AE of the same type, determined to be related to study vaccine, that persists for 72 hours or longer; *OR*
5. Death of a subject, regardless of causality.

After the first DRC meeting triggered by the occurrence of a given pausing rule, the DRC will convene thereafter for each additional subject meeting that pausing rule.

The DRC will review blinded safety data first, but is entitled to and has the right to require submission of unblinded data if deemed necessary.

Resumption of vaccinations will start only upon receipt by the study site of written recommendations by the DRC. These communications from the DRC will be forwarded by the investigator to the IRB/IEC and by the sponsor to the relevant health authorities.

To enable prompt response to a situation that would trigger pausing rules 3, 4 or 5, the investigator should update the eCRF with information on any Grade 3 or 4 AE on the same day that the AE is reported.

12. ADVERSE EVENT REPORTING

Timely, accurate, and complete reporting and analysis of safety information from clinical studies are crucial for the protection of subjects, investigators, and the sponsor, and are mandated by regulatory agencies worldwide. The sponsor has established standard operating procedures in conformity with regulatory requirements worldwide to ensure appropriate reporting of safety information; all clinical studies conducted by the sponsor or its affiliates will be conducted in accordance with those procedures.

Method of Detecting Adverse Events and Serious Adverse Events

Care will be taken not to introduce bias when detecting AEs or SAEs. Open-ended and non-leading verbal questioning of the subject is the preferred method to inquire about AE occurrence. For some studies, subjects are not always able to provide valid verbal responses to open-ended questions. In these circumstances, another method of detecting these events is specified.

Solicited Adverse Events

Solicited AEs are pre-defined local (at the Ad26.RSV.preF [or placebo] and seasonal influenza vaccine injection sites) and systemic events for which subjects are specifically questioned and which are noted by subjects in their diary (see Section 9.1.1).

Unsolicited Adverse Events

Unsolicited AEs are all AEs for which subjects are specifically not questioned in the subject diary.

12.1. Definitions

12.1.1. Adverse Event Definitions and Classifications

Adverse Event

An AE is any untoward medical occurrence in a clinical study subject administered a medicinal (investigational or non-investigational) product. An AE does not necessarily have a causal relationship with study vaccine. An AE can therefore be any unfavorable and unintended sign (including an abnormal finding), symptom, or disease temporally associated with the use of a medicinal (investigational or non-investigational) product, whether or not related to that medicinal (investigational or non-investigational) product (Definition per International Conference on Harmonisation [ICH]).

This includes any occurrence that is new in onset or aggravated in severity or frequency from the baseline condition, or abnormal results of diagnostic procedures, including laboratory test abnormalities.

Note: The sponsor collects unsolicited AEs starting from ICF signature for 28 days after the second vaccination, and solicited AEs from the time of each vaccination for 7 days post-vaccination (refer to Section 12.3.1 for time of last AE recording). SAEs will be collected from ICF signature for the duration of the study. RTIs, preferably as a diagnosis, will be reported on the AE page of the eCRF if they occur between first vaccination and 28 days following the second vaccination; any RTI fulfilling the criteria of an SAE would be reported as such during the entire study period.

Serious Adverse Event

An SAE based on ICH and EU Guidelines on Pharmacovigilance for Medicinal Products for Human Use is any untoward medical occurrence that at any dose:

- Results in death
- Is life-threatening
(The subject was at risk of death at the time of the event. It does not refer to an event that hypothetically might have caused death if it were more severe)
- Requires inpatient hospitalization or prolongation of existing hospitalization
- Results in persistent or significant disability/incapacity
- Is a congenital anomaly/birth defect
- Is a suspected transmission of any infectious agent via a medicinal product
- Is Medically Important*

*Medical and scientific judgment should be exercised in deciding whether expedited reporting is also appropriate in other situations, such as important medical events that may not be

immediately life-threatening or result in death or hospitalization but may jeopardize the subject or may require intervention to prevent one of the other outcomes listed in the definition above. These should usually be considered serious.

If a serious and unexpected AE occurs for which there is evidence suggesting a causal relationship between study vaccine and the event (eg, death from anaphylaxis), the event must be reported as a suspected unexpected serious adverse reaction (SUSAR) by the sponsor to health authorities and by the investigator to the IRB/IEC according to regulatory and local requirements.

Unlisted (Unexpected) Adverse Event/Reference Safety Information

An AE is considered unlisted if the nature or severity is not consistent with the applicable product reference safety information. For Ad26.RSV.preF, the expectedness of an AE will be determined by whether or not it is listed in the Investigator's Brochure.¹

For Fluarix, the expectedness of an AE will be determined by whether or not it is listed in the package insert.

Adverse Event Associated With the Use of the Vaccine

An AE is considered associated with the use of study vaccine if the attribution is related by the definitions listed in Section 12.1.2.

12.1.2. Attribution Definitions

Every effort should be made by the investigator to explain any AE and assess its potential causal relationship, ie, to administration of study vaccine or to alternative causes (eg, natural history of the underlying diseases, concomitant therapy). This applies to all AEs, whether serious or non-serious.

Causality of AEs should be assessed by the investigator based on the following:

Related: there is suspicion that there is a relationship between study vaccine and the AE (without determining the extent of probability); there is a reasonable possibility that study vaccine contributed to the AE.

Unrelated: there is no suspicion that there is a relationship between study vaccine and the AE; there are other more likely causes and administration of study vaccine is not suspected to have contributed to the AE.

By definition, all solicited AEs at the injection site (local) will be considered related to study vaccine administration.

12.1.3. Severity Criteria

All AEs will be coded for severity using the toxicity grading table in [Attachment 1](#). For AEs not identified in the grading table, the following guidelines will be applied:

Mild (Grade 1): No interference with activity.

Moderate (Grade 2): Some interference with activity not requiring medical intervention.

Severe (Grade 3): Prevents daily activity and requires medical intervention.

Potentially life-threatening (Grade 4): Symptoms causing inability to perform basic self-care functions OR medical or operative intervention indicated to prevent permanent impairment, persistent disability.

The investigator should use clinical judgment in assessing the severity of events not directly experienced by the subject (eg, laboratory abnormalities).

The severity of solicited AEs will be graded in the diary by the subject based on the severity assessment provided in the diary and then verified by the investigator using the FDA toxicity grading table (see [Attachment 1](#)).

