Nausea/vomiting	No interference with activity or 1 - 2 episodes/24 hours	Some interference with activity or >2 episodes/24 hours	Prevents daily activity, requires outpatient IV hydration	ER visit or hospitalization for hypotensive shock
Diarrhea	2 - 3 loose stools or <400 gms/24 hours	4 - 5 stools or 400 - 800 gms/24 hours	6 or more watery stools or >800gms/24 hours or requires outpatient IV hydration	ER visit or hospitalization
Headache	No interference with activity	Repeated use of non-narcotic pain reliever >24 hours or some interference with activity	Significant; any use of narcotic pain reliever or prevents daily activity	ER visit or hospitalization
Fatigue	No interference with activity	Some interference with activity	Significant; prevents daily activity	ER visit or hospitalization
Myalgia	No interference with activity	Some interference with activity	Significant; prevents daily activity	ER visit or hospitalization
Systemic Illness	Mild (Grade 1)	Moderate (Grade 2)	Severe (Grade 3)	Potentially Life-threatening (Grade 4)
Illness or clinical adverse event (as defined according to applicable regulations)	No interference with activity	Some interference with activity not requiring medical intervention	Prevents daily activity and requires medical intervention	ER visit or hospitalization

INVESTIGATOR AGREEMENT

I have read this protocol and agree that it contains all necessary details for carrying out this study. I will conduct the study as outlined herein and will complete the study within the time designated.

I will provide copies of the protocol and all pertinent information to all individuals responsible to me who assist in the conduct of this study. I will discuss this material with them to ensure that they are fully informed regarding the study vaccine, the conduct of the study, and the obligations of confidentiality.

Coordinating Investigator (where required):

Name (typed or printed): _____

Institution and Address: _____

Signature: _____ Date: _____
(Day Month Year)

Principal (Site) Investigator:

Name (typed or printed): _____

Institution and Address: _____

Telephone Number: _____

Signature: _____ Date: _____
(Day Month Year)

Sponsor's Responsible Medical Officer:

Name (typed or printed): [name]

Institution: Janssen Vaccines & Prevention B.V.

Signature: electronic signature appended at the end of the protocol Date: _____
(Day Month Year)

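### Chills and arthralgia have no grading row of their own, so an episode that stops daily activity without medical intervention does not clearly reach Grade 3 and may not count toward pausing rule 4

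*Protocol*

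**What the plan says.** Section 9.2.2.1 of the protocol lists the solicited systemic AEs as fatigue, headache, myalgia, arthralgia, chills, nausea and fever, and has the investigator grade them by section 12.1.3.

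Section 12.1.3 puts Attachment 1 first: "All AEs will be coded for severity using the toxicity grading table in" that attachment. It then adds a fallback: "For AEs not identified in the grading table, the following guidelines will be applied". Two steps of the fallback matter here:

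- "Moderate (Grade 2): Some interference with activity not requiring medical intervention"
- "Severe (Grade 3): Prevents daily activity and requires medical intervention"

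The Systemic Illness row at the end of Attachment 1 uses the same wording for Grades 1 to 3. For solicited AEs the subject grades first in the diary, and the grade is "then verified by the investigator using the FDA toxicity grading table".

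Attachment 1 has its own rows for fever, nausea/vomiting, headache, fatigue and myalgia. It has none for chills or arthralgia. In the fatigue and myalgia rows Grade 3 is "Significant; prevents daily activity", with no condition about care. The headache row also accepts loss of daily activity as sufficient.

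Pausing rule 4 in section 11.8 is triggered when at least two subjects have a related Grade 3 or 4 solicited systemic AE of the same type lasting 72 hours or longer. Rule 3 does the same for unsolicited AEs. Section 11.5 tabulates solicited AEs by severity.

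**The concern.** Under rule 4 the grade is the trigger. If two solicited symptoms are graded on a scale with a stricter Grade 3 than their neighbours, equal disability is treated differently. Three days of joint pain that keep a subject from normal activities, managed at home, may not count, while three days of equally disabling muscle pain do.

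The two terms are expected reactions. Section 1.1 names chills among the most common solicited systemic AEs after the earlier Ad26 RSV vaccine, and section 16.1 lists chills and joint pain among the events reported after Ad26-vectored vaccines. The protocol gives no reason for a higher bar for them. The severity tables for these terms carry the same ambiguity, as does the duty in section 11.8 to enter Grade 3 or 4 AEs in the eCRF on the day they are reported.

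**Working it through.** The plan states no figure to reproduce, so the check is a literal reading of the definitions.

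**Step 1: where each solicited systemic term is graded**

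| Term | Attachment 1 row | Is loss of daily activity alone Grade 3? |
|---|---|---|
| Headache, fatigue, myalgia (3) | yes | yes |
| Fever (1) | yes | graded by temperature |
| Nausea (1) | yes | unclear; the row links loss of activity and outpatient IV hydration by a comma |
| Chills, arthralgia (2) | none | no; the general scale applies |

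The count is 3 + 1 + 1 + 2 = 7 terms.

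**Step 2: general scale against the myalgia row**

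Take events with self-care intact and no emergency-room visit. Three levels of interference by two levels of care give 3 × 2 = 6 combinations.

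| Effect on activity | Care | General scale | Myalgia row |
|---|---|---|---|
| none | none | 1 | 1 |
| none | outpatient | 1 | 1 |
| some | none | 2 | 2 |
| some | outpatient | no grade fits | 2 |
| prevented | none | **no grade fits** | **3** |
| prevented | outpatient | 3 | 3 |

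The section 12.1.3 list and the Systemic Illness row give the same result in all 6, so it does not matter here which of them governs. Two combinations have no grade. Only the one with activity prevented and no care bears on rule 4, because the other is Grade 2 under the myalgia wording. Grade 3 covers 1 of the 6 combinations on the general scale and 2 of 6 in the myalgia row.

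**Step 3: does another clause settle the grade?**

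The clinical-judgment sentence in section 12.1.3 covers events that the subject does not directly experience, such as laboratory findings, so it does not reach chills or joint pain. Verification of the diary grade leads back to Attachment 1, which has no row for either.

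**Step 4: illustration under assumed rates**

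Neither rate below is in the protocol. Let p be the true rate, among 180 subjects, of a related, activity-preventing episode of one type lasting 72 hours or longer. Let f be the share of these that need medical intervention. If only that share is counted, q = p × f, and P(at least 2) = 1 − (1 − q)^180 − 180·q·(1 − q)^179.

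| p | f = 10% | f = 25% | f = 50% | all counted |
|---|---|---|---|---|
| 1% | 0.01 | 0.08 | 0.23 | 0.54 |
| 2% | 0.05 | 0.23 | 0.54 | 0.88 |
| 5% | 0.23 | 0.66 | 0.94 | >0.99 |

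This is the worst case, in which no unclear episode is ever graded 3. It shows the direction of the effect and does not estimate how often it would occur.

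**The case against.** The strongest reply is that severity grades are ordered levels applied by a clinician. Section 12.3.1 has the investigator determine severity and identify events that invoke the pausing rules. Faced with arthralgia that stops daily activity, an investigator would choose Grade 2 or 3 and would not leave the field blank. This stands: the practical risk is inconsistent grading between 2 and 3, not a missing grade.

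The diary contains severity scales (section 9.1.1) that are not shown and may cover both terms. This also stands in part, although the investigator still has to verify the diary grade against a table without these rows.

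Vaccination can also be suspended for significant safety concerns (section 11.8), and AEs of concern go to the DRC (section 11.7). Both routes are real, but they rest on judgment, whereas the numbered rules are there to give fixed thresholds.

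The general wording was also a deliberate choice: the rationale for Amendment 1 says it was aligned with the FDA criteria. A reader might infer that the general scale is simply an error and must be rewritten for all unsolicited AEs. The protocol does not support that. The choice is stated, and changing it is optional.

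A reader might further infer that pausing rule 1 is undermined, because Grade 4 is defined differently in section 12.1.3 and in the Systemic Illness row. That goes too far. Related SAEs and all deaths pause vaccination on either definition. What remains is a small group of related non-serious events without their own row, mainly emergency visits without admission, and the protocol does not show which definition should prevail.

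**Conclusion.** The point holds as a minor one. For 2 of the 7 solicited systemic AEs, an activity-preventing episode without medical intervention has no clear grade, while the same degree of disability is Grade 3 for myalgia, fatigue and headache. It may therefore be missed by rule 4 and in the severity tables.

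This rests on reading the definitions as written, with self-care intact and no emergency visit. How often such episodes would occur, and what the diary says, cannot be known from the protocol. It would be wrong to conclude that these reactions could never pause the study, since judgment-based routes exist. Nor is there ground for inferring bias between the groups: both are graded on the same scale by staff blinded to Ad26.RSV.preF, and safety is analysed descriptively. No sample size, power or alpha figure changes.

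**What to change.** Add two rows to Attachment 1, for chills and for arthralgia, repeating all four cells of the myalgia row, so that Grade 3 reads "Significant; prevents daily activity". Put matching text in the subject diary.

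Optionally, for unsolicited AEs under rule 3, state in section 12.1.3 and in the Systemic Illness row that loss of daily activity is Grade 3 with or without medical intervention. The amendment should note that this departs from the FDA wording adopted in Amendment 1.

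The cost is amendment and diary wording, and possibly a few more pausing-rule reviews by the DRC.

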12.2. Special Reporting Situations

Safety events of interest on a sponsor study vaccine that may require expedited reporting and/or safety evaluation include, but are not limited to:

- Suspected abuse/misuse of a sponsor study vaccine
- Accidental or occupational exposure to a sponsor study vaccine
- Medication error involving a sponsor product (with or without subject/patient exposure to the sponsor study vaccine, eg, name confusion)
- Exposure to a sponsor study vaccine from breast-feeding

Special reporting situations should be recorded in the eCRF. Any special reporting situation that meets the criteria of an SAE should be recorded on the Serious Adverse Event page of the eCRF.

12.3. Procedures

12.3.1. All Adverse Events

Unsolicited AEs and special reporting situations will be reported from the time a signed and dated ICF is obtained until 28 days (including relevant visit window, if applicable) after the second vaccination.

Solicited AEs will be recorded by each subject in the subject diary for 7 days after each dosing. The investigator will review each subject's diary at the subsequent site visit; diary information will be transcribed by the study personnel in the on-site assessment forms in the eCRF.

The sponsor will evaluate any safety information that is spontaneously reported by an investigator beyond the time frame specified in the protocol.

The investigator will monitor and check the study data including all AE data as they become available and will make determinations regarding the severity of the adverse experiences and their relation to study vaccine. All AEs will be deemed related to study vaccine or not related to study vaccine, according to Section 12.1.2.

The investigator must review both post-injection reactogenicity and other AEs to insure the prompt and complete identification of all events that require expedited reporting as SAEs, invoke pausing rules or are other serious and unexpected events.

All AEs, regardless of seriousness, severity, or presumed relationship to study vaccine, must be recorded using medical terminology in the source document and the eCRF. Whenever possible, diagnoses should be given when signs and symptoms are due to a common etiology (eg, cough, runny nose, sneezing, sore throat, and head congestion should be reported as “upper respiratory infection”). Investigators must record in the eCRF their opinion concerning the relationship of the AE to study vaccine. All measures required for AE management must be recorded in the source document and reported according to sponsor instructions.

The sponsor assumes responsibility for appropriate reporting of AEs to the regulatory authorities. The sponsor will also report to the investigator (and the head of the investigational institute where required) all SUSARs. The investigator (or sponsor where required) must report SUSARs to the appropriate IEC/IRB that approved the protocol unless otherwise required and documented by the IEC/IRB. A SUSAR will be reported to regulatory authorities unblinded. Participating investigators and IEC/IRB will receive a blinded SUSAR summary, unless otherwise specified.

Each subject will be provided with a “wallet (study) card” and instructed to carry this card with them for the duration of the study indicating the following:

- Study number
- Statement, in the local language(s), that the subject is participating in a clinical study
- Investigator’s name and 24-hour contact telephone number
- Local sponsor’s name and 24-hour contact telephone number (for medical staff only)
- Site number
- Subject number
- Any other information that is required to do an emergency breaking of the blind

